#### 5.3.2. **Leukocytosis**

Patients who develop leukocytosis on study drug will be administered hydroxyurea at a dose of 500 mg qid for WBC between 20,000 and 50,000/ $\mu$ L and 1 g qid for WBC >50,000/ $\mu$ L. Hydroxyurea may be considered for a WBC between 10,000 and 20,000/ $\mu$ L on a case by case basis, in consultation with the study PI. Hydroxyurea can be discontinued when WBC returns below 10-20,000/ $\mu$ L, per the judgment of the investigator, and must be stopped with WBC <5,000/ $\mu$ L. If a consistent need for hydroxyurea persists beyond induction therapy, the patient will be withdrawn from the protocol.

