### 5.6. **Criteria for removal from study:**

Patients will be removed from study when any of the criteria listed in Sections 3.5, 5.2, and 5.4 applies. The reason for study removal and the date the patient was removed will be documented in the Case Report Form.

Some patients may have improvement in their baseline PB counts, including a decrease in peripheral blasts following the start of IRX5183 dosing. It is also possible that peripheral counts will worsen or the number of BM blasts will increase with the initiation of therapy. In some cases, patients will not have had sufficient time to develop the required amount of differentiation to impact the counts. It is also possible that increases in blasts or other disease parameters may represent differentiation of leukemia cells in response to IRX5183. In conventional studies, such changes may be worrisome for PD and lead to the premature discontinuation of study drug. Patients with minor blast increases (defined as an increase of  $\leq 50\%$  of baseline bone marrow blast count) or worsening PB counts *prior to* week 8 may continue on study provided that they remain stable clinically. Primary tumor assessments will be made using IWG 2003 and IWG 2006 criteria at the completion of induction therapy (**Appendix A1-A3**).

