### **7.3. Measurement of Response / Response Criteria:**

The primary endpoint of clinical response is defined by the International Working Group recommendations (see Appendix A1-A3) for therapeutic trials in AML and MDS and includes CR, complete remission with incomplete count recovery (CRi, formerly known as morphologic leukemia-free state or marrow CR), partial remission (PR), HI, SD, and PD (Cheson et al., 2003). We will also include an assessment of HI per MDS IWG-2006 recommendations as one of our secondary endpoints in our AML patients (see Appendix A2). In addition to the criteria in Appendix A1, the following will be considered as PD:

- 1) A significant increase in bone marrow blasts beyond 4 weeks of starting the drug:
  - a. if baseline 51-100% blasts – an increase of greater than 50% of baseline
  - b. if baseline 26-50% blasts – an increase up to 2 x the baseline
  - c. if baseline 0-25% blasts – an increase up to 3 x the baseline
- 2) A rising peripheral WBC after adequate dosing with hydroxyurea (see section 5.3 above)

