#### 9.2.4. Differentiation syndrome (DS):

DS is a common occurrence in patients with APL treated with ATRA. The syndrome has been defined by the presence of the following signs or symptoms: unexplained fever, dyspnea, pleural and/or pericardial effusion, pulmonary infiltrates, renal failure, hypotension, and unexplained weight gain greater than 5 kg, and graded based on the number of these findings (Montesinos et al., 2009). Patients with 4 or more of the aforementioned signs or symptoms are classified as having severe DS, whereas those with 2 or 3 signs or symptoms are classified as having moderate DS. This condition is best treated with high dose dexamethasone at a dose of 10 mg IV twice daily.

Grade 1 DS per CTCAE v4 is defined as “fluid retention; <3 kg of weight gain; intervention with

fluid restriction and/or diuretics indicated.” Grade 2 is defined as “moderate signs or symptoms; steroids indicated.” Grade 3 is defined as “severe symptoms; hospitalization indicated.” Grade 4 is defined as “life-threatening consequences; ventilator support indicated.” The definition per CTCAE is “a disorder characterized by weight gain, dyspnea, pleural and pericardial effusions, leukocytosis and/or renal failure originally described in patients treated with all-trans retinoid acid.”

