### **11.8.2. Evaluation of response:**

All patients included in the study that complete 2 cycles of therapy will be assessed for response to treatment, even if there are major protocol treatment deviations or if they are ineligible. The primary endpoint to the dose expansion phase is response per IWG criteria after receiving at least 2 cycles of therapy. Only those patients who have measurable disease present at baseline, have received at least 2 cycles of therapy, and have had their disease re-evaluated will be considered evaluable for response. These patients will have their response classified according to the definitions stated in Appendix A. Patients who exhibit objective disease progression prior to the end of cycle 2 will be considered not evaluable and will be taken off study.

An incorrect treatment schedule or drug administration does not result in exclusion from the analysis of the response rate. Patients with disease progression, death due to their disease, and death due to toxicity prior to completion of induction therapy will be excluded from the primary analysis. This will prevent dismissal of an active drug based on progression in patients with highly refractory disease who are unable to receive enough of the drug to see a clinical benefit. Patients who are unable to complete induction therapy for any reason will be treated as missing data and additional patients will be recruited in their place to reach our target sample size of 27 for phase II.

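### Section 7.3 counts a rising WBC after hydroxyurea as progression with no time limit or exception for differentiation, sections 5.3.2 and 5.6 can point the other way before week 8, and the evaluable set for phase II depends on which is followed

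*Combined protocol and SAP*

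**What the plan says.** - **Section 7.3** introduces two further progression rules with the words "In addition to the criteria in Appendix A1, the following will be considered as PD". Item 1 concerns marrow and carries a time limit: "A significant increase in bone marrow blasts beyond 4 weeks of starting the drug". Item 2 is "A rising peripheral WBC after adequate dosing with hydroxyurea (see section 5.3 above"). The limit in item 1 is not repeated in item 2.
- **Section 5.3.2** treats leukocytosis on study drug with hydroxyurea: one tier for a WBC of 20,000 to 50,000/µL and a higher tier above 50,000/µL. Its own withdrawal rule is "If a consistent need for hydroxyurea persists beyond induction therapy, the patient will be withdrawn from the protocol".
- **Section 5.6** warns: "It is also possible that increases in blasts or other disease parameters may represent differentiation of leukemia cells in response to IRX5183". Patients with minor blast increases (at most 50% of baseline) or worsening peripheral counts before week 8 "may continue on study provided that they remain stable clinically".
- **Section 3.5** lists progression under Appendix A and section 7.3 as a reason for coming off study.
- **Section 11.8.2** states: "Patients who exhibit objective disease progression prior to the end of cycle 2 will be considered not evaluable and will be taken off study". It also excludes these patients from the primary analysis and replaces anyone who does not complete induction, until 27 is reached.
- **Section 11.1** sets the decision rules: at least 1 response in 13 to continue, and at least 4 in 27 to be encouraging.

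**The concern.** The drug is meant to make leukemic cells mature, and the protocol expects that this may disturb the blood counts. Section 9.2.4 quotes a CTCAE description of differentiation syndrome that includes "weight gain, dyspnea, pleural and pericardial effusions, leukocytosis and/or renal failure". Section 8.1 treats mature neutrophils carrying the malignant abnormality in blood as evidence of differentiation, and section 11.7 uses the ANC as a marker of it. A rule based on total WBC cannot separate such cells from blasts.

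The rule carries weight in AML. Appendix A1 lists response, treatment failure and relapse but has no progression category, so section 7.3 supplies the only explicit progression criteria for these patients. Section 5.1 says a first response to retinoids can take up to 60 days, whereas item 2 can apply from the first weeks.

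At stake is whether two patients with the same blood counts are handled alike: one treated to the assessment after cycle 2 and counted, the other removed, left out of the primary analysis and replaced.

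**Working it through.** **1. The passages side by side.** Take an AML patient in week 3 whose WBC moves from the 20,000 to 50,000/µL band to above 50,000/µL while on hydroxyurea, and who is clinically stable.

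| Passage | Consequence |
|---|---|
| 5.3.2 | Higher hydroxyurea tier; stated withdrawal only for a need that outlasts induction |
| 5.6 | May continue, if a rising WBC counts as worsening peripheral counts |
| 7.3 item 2 | Progression, if the first tier counts as adequate |
| 3.5 and 11.8.2 | If progression: off study, not evaluable, replaced |

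Neither rising nor adequate is defined beyond the pointer to 5.3, and no order of precedence is given.

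**2. The plan's own design.** Inputs from 11.1: n1 = 13, n = 27, response rates 0.05 and 0.20, type I error 0.05, power 0.8. With b(x; 13, p) the binomial probability,

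P(positive) = Σ over x = 1 to 13 of b(x; 13, p) × P(Bin(14, p) ≥ max(0, 4 − x)); P(stop at stage 1) = (1 − p)^13.

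- p = 0.05: P(positive) = 0.0416, P(stop) = 0.513.
- p = 0.20: P(positive) = 0.8011, P(stop) = 0.055.

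The stated design reproduces and is not in question.

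**3. Removed patients are would-be responders.** Assume a true response rate of 20% of all treated, and that a share w of all treated are responders called progression and replaced. The evaluable rate is (0.20 − w)/(1 − w).

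| w (assumed) | Evaluable rate | Power | P(stop at stage 1) |
|---|---|---|---|
| 0 | 20.0% | 80.1% | 5.5% |
| 5% | 15.8% | 61.8% | 10.7% |
| 10% | 11.1% | 33.9% | 21.6% |
| 15% | 5.9% | 6.8% | 45.5% |

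**4. Removed patients are all non-responders.** Assume a true response rate of 5% of all treated and a share f removed and replaced. The evaluable rate is 0.05/(1 − f).

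| f (assumed) | Evaluable rate | False-positive chance |
|---|---|---|
| 0 | 5.0% | 4.2% |
| 10% | 5.6% | 5.7% |
| 20% | 6.3% | 8.1% |
| 30% | 7.1% | 11.8% |

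**5. Where the bias changes sign.** Assume 30% removed, a true rate of 20%, and a share s of those removed who would have responded. The evaluable rate is (0.20 − 0.30s)/0.70. Power is 96.4%, 80.1%, 61.4% and 11.8% for s = 0, 20%, 30% and 50%. The bias is zero when the removed patients would have responded as often as everyone else (s = 20%), and its sign depends on which side of that they fall.

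**The case against.** The passages can be read as a sequence: 5.3.2 treats leukocytosis, and 7.3 applies when the WBC still rises after that treatment. The week-8 permission in 5.6 can also be read as an exception to the removal criteria it follows. Both readings are reasonable, but neither is written down. The first leaves the move from the lower to the higher hydroxyurea tier unresolved; the second does not switch off 11.8.2.

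Several stronger readings are tempting, and the documents do not support them:

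- *Any WBC rise is progression.* Item 2 requires adequate hydroxyurea first.
- *Sections 5.3.2 and 5.6 keep the patient on study as possible differentiation.* Section 5.3.2 never mentions differentiation. Section 5.6 permits rather than requires continuation, demands clinical stability and does not name WBC.
- *The rule covers all patients.* It is worded as an addition to Appendix A1, which is the AML appendix; its reach to MDS is not stated.
- *Item 2 distorts time to progression.* Sections 5.4 and 7.2 item 14 define progression by Appendix A1-A2 only. What stands is that progression for coming off study and progression for the time-to-event endpoint can differ.
- *Leukocytosis always signals differentiation.* The sign-and-symptom list in 9.2.4 omits it; only the CTCAE description there includes it.

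Two more points are fair. Exclusion and replacement come from 11.8.2 and apply to all early progression, not only to item 2. Section 11.7 already promises a response report in all eligible patients; but it does not say how patients removed early are counted, and 11.8.2 builds the target of 27 from patients who complete induction.

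**Conclusion.** The concern holds as an unreconciled conflict with consequences for the analysis. Item 2 has no time limit, cell type or exception for differentiation; 5.6 and 5.3.2 can point the other way for the same patient before week 8; and the evaluable set behind both Simon decisions depends on the passage followed.

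Its size cannot be fixed, because the documents give no rate for a WBC rise despite hydroxyurea. The tables show ranges under assumed rates and are not estimates. A reader might apply an assumed 5% to 20% leukocytosis rate to 27 patients and get 1 to 5 (0.05 × 27 = 1.35; 0.20 × 27 = 5.4). That does not stand: leukocytosis is a broader event than item 2, and replaced patients are never among the 27. A reader might also infer that the rule always works against the drug. It does not: power is lost if would-be responders are removed, and the response rate is inflated if only non-responders are.

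**What to change.** 1. Reconcile 5.3.2, 5.6, 7.3 item 2 and 11.8.2, and state which governs before week 8. The clinical rule is for the sponsor and investigators to settle. A split of blasts as progression and mature cells as not would itself set a stopping rule, and would clash with the statement in 5.6 that blast increases may be differentiation, so it is not proposed here.
2. Define rising and adequate dosing in item 2. State whether the WBC differential, already collected twice weekly in cycle 1 and at least weekly in cycle 2, is used, and whether the item covers MDS.
3. Use one progression definition across 3.5, 5.4, 7.2 item 14 and 7.3.
4. Report, as a sensitivity analysis, the response rate with patients removed under item 2 before the end of cycle 2 counted as non-responders. This guards against inflation only. It does not recover lost responders: with 27 patients and w = 5%, the rate is 0.20 − 0.05 = 0.15 and power is 57.5%. Only step 1 addresses that side.

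Cost: a wording amendment and one extra analysis, with no new tests.

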### **7.4. Adverse Events:**

An adverse event (AE) is defined as any untoward medical occurrence in a patient or clinical investigation subject administered a pharmaceutical product and which does not necessarily have a causal relationship with treatment. An AE can therefore be any unfavorable and unintended sign (including an abnormal laboratory finding), symptom, or disease temporally associated with the use of a medicinal (investigational) product, whether or not considered related to the medicinal (investigational) product.

AEs are to be coded using an internationally recognized dictionary.

This study will utilize the Common Toxicity Criteria (CTC) version 4.0 for toxicity where applicable and adverse event reporting. In cases where CTC cannot be applied to the toxic event, the investigator will quantify the toxicity based on intensity, as per section 14.1 below.

Patients are to be followed for adverse events for 30 days after the last dose of study drug. Any adverse event occurring in a patient 30 days after stopping the study drug must be reported. The

period after discontinuing study drug may be extended if there is a strong suspicion that the drug has not yet been eliminated or if the nature of the event may suggest long-term effects by the investigational drug, as assessed by the investigator.

#### **7.5. Serious Adverse Event (SAE):**

An SAE is defined in the FDA CFR 312 as any adverse drug experience occurring at any dose that results in any of the following outcomes: death, a life-threatening adverse drug experience, inpatient hospitalization, or prolongation of existing hospitalization, a persistent or significant disability/incapacity, or a congenital anomaly/birth defect. Important medical events that may not result in death, be life threatening, or require hospitalization may be considered a serious adverse drug experience when, based upon medical judgment, they may jeopardize the patient or subject and may require medical or surgical intervention to prevent one of the outcomes listed in this definition.

#### **7.6. Toxicity Reporting:**

Toxicity scores will be assigned using the NCI Common Toxicity Criteria version 4.0 twice weekly by the attending or research nurse through the initial cycle of therapy and weekly thereafter. A copy of the CTC version 4.0 can be downloaded from CTEP online ([http://ctep.cancer.gov/protocolDevelopment/electronic\\_applications/ctc.htm](http://ctep.cancer.gov/protocolDevelopment/electronic_applications/ctc.htm)). If an unexpected and serious toxicity is seen that results in patients being subjected to unacceptable risk, the trial will be placed on hold while this toxicity is investigated.

#### **7.7. Toxicity Monitoring:**

The Principal Investigator is responsible for the ongoing safety evaluation of the study and shall provide to Io Therapeutics, Inc. all Serious Adverse Events (SAEs) within 24 hours of the Principal Investigator's awareness. All fatal and life-threatening events will be reported immediately by phone. A written report will be submitted within ten working days. The first occurrence of any previously unexpected clinical event, regardless of grade, will be reported by phone within 24 hours. A written report is also required. Unexpected SAEs are defined as those adverse effects not described in the Io therapeutics investigator's brochure. Drug-related SAEs are defined as those adverse events that indicate a possible, probably, or likely relationship between IRX5183 administration and the SAE. In addition to standard reporting to the FDA and clinical trials network, SAEs will be reported to Io Therapeutics, Inc. within 24 hours of the awareness of the SAE. The following guidelines are recommended for phase II studies:

**Phase 1 and Early Phase 2 Studies: Expedited Reporting Requirements for Adverse Events that Occur on Studies under an IND/IDE within 30 Days of the Last Administration of the Investigational Agent/Intervention**

FDA REPORTING REQUIREMENTS FOR SERIOUS ADVERSE EVENTS (21 CFR Part 312)		

NOTE: Investigators MUST immediately report to the sponsor (NCI) ANY Serious Adverse Events, whether or not they are considered related to the investigational agent(s)/intervention (21 CFR 312.64)
 
An adverse event is considered serious if it results in ANY of the following outcomes:
 
Death
 
A life-threatening adverse event
 
An adverse event that results in inpatient hospitalization or prolongation of existing hospitalization for <math>\geq</math> 24 hours
 
A persistent or significant incapacity or substantial disruption of the ability to conduct normal life functions
 
A congenital anomaly/birth defect.
 
Important Medical Events (IME) that may not result in death, be life threatening, or require hospitalization may be considered serious when, based upon medical judgment, they may jeopardize the patient or subject and may require medical or surgical intervention to prevent one of the outcomes listed in this definition. (FDA, 21 CFR 312.32; ICH E2A and ICH E6).
		

ALL SERIOUS adverse events that meet the above criteria MUST be immediately reported to the NCI via CTEP-AERS within the timeframes detailed in the table below.
		
Hospitalization	Grade 1 and Grade 2 Timeframes	Grade 3-5 Timeframes
Resulting in Hospitalization $\geq$ 24 hrs	10 Calendar Days	24-Hour 5 Calendar Days
Not resulting in Hospitalization $\geq$ 24 hrs	Not required	

Expedited AE reporting timelines are defined as:
 
 
○ “24-Hour; 5 Calendar Days” - The AE must initially be reported via CTEP-AERS within 24 hours of learning of the AE, followed by a complete expedited report within 5 calendar days of the initial 24-hour report.
 
○ “10 Calendar Days” - A complete expedited report on the AE must be submitted within 10 calendar days of learning of the AE.
 
		

Serious adverse events that occur more than 30 days after the last administration of investigational agent/intervention and have an attribution of possible, probable, or definite require reporting as follows:
 
Expedited 24-hour notification followed by complete report within 5 calendar days for:
 
 
• All Grade 3, 4, and Grade 5 AEs
 
 
Expedited 10 calendar day reports for:
 
 
• Grade 2 AEs resulting in hospitalization or prolongation of hospitalization
 
 
 For studies using PET or SPECT IND agents, the AE reporting period is limited to 10 radioactive half-lives, rounded UP to the nearest whole day, after the agent/intervention was last administered. Footnote “1” above applies after this reporting period.
 
Effective Date: May 5, 2011
		

## 7.8. Pharmacokinetics:

In phase I, we plan to first determine pharmacokinetic (PK) parameters of IRX5183 on days 1 and 14 ( $\pm$ 3) of cycle 1 in the PB and BM compartments (may be obtained post cycle 1 if day 14 BM specimen not available). In phase II, we will perform confirmatory testing at these time points in a subgroup of patients. Full sampling, processing, storage, and shipment instructions will be provided in the Laboratory manual. Briefly, trough and peak levels of IRX5183 will be determined in the plasma and mononuclear cells (MNC) by obtaining a 4 mL sample of blood (green top tubes-sodium heparin)  $\frac{1}{2}$  hour before the morning dose and then 2 hours ( $\pm$  30 minutes) post drug administration. Phase I PK data showed that  $T_{max}$  generally was in the range of 1-3 hours post dose across individual patients. We will isolate platelet rich plasma (PRP) and

MNC and samples will be frozen in our laboratory, and then shipped and analyzed in a batch on dry ice to the laboratory of [name] at the University of Maryland. Drug levels will be determined by liquid chromatography mass spectroscopy (LCMS), per techniques as previously reported (Kane, 2012).

Peak drug levels will also be determined in the BM compartment on day 14 ( $\pm$  3 days) (may be obtained post cycle 1 if day 14 BM specimen not available), approximately 1 to 3 hours after dosing (as close to 2 hours post as possible, but up to 4 hours post drug administration). We will allow for flexibility in timing of the BM due to difficulties with scheduling and wait times, but we will aim for collection as close to that of the PB as possible, for optimal comparison of drug concentrations. We are interested to see whether intracellular levels will differ between LSCs, normal hematopoietic stem cells (HSCs), and bulk AML cells, and how these levels compare to plasma. We will isolate BM plasma and MNC from the BM aspirate and sort for LSCs, normal HSCs, and bulk AML (when possible) and then freeze at -80 degrees Celsius (as per the Lab Manual and section 8.2 below). Depending on the type of AML, we may not be able to isolate CD34+CD38ALDHint LSCs, in which case we will isolate CD34+CD38 cells. Samples will be shipped and analyzed in a batch at the end of the study by LCMS in the laboratory of [name], as above.

If for any reason during enrollment on the trial, a patient requires a lumbar puncture, we will obtain a specimen for measurement of IRX5183 levels, in order to determine whether the drug penetrates the blood brain barrier. We would obtain 2 mL CSF to be frozen and sent to [name] on dry ice for analysis by LCMS. We would also collect a 4 mL sample of PB (green top tube-sodium heparin) at the same time point, isolating and freezing PRP and MNC as above. See lab manual for details on processing, storage, and shipment instructions.

